6.2. KEY DEFINITIONS

6.2.1. Baseline Values

Unless otherwise specified, baseline is defined as:

- For study 603A endpoints, baseline is defined as the last non-missing measurement prior to the first dose of double-blind study medication in 603A.
- For study 603B endpoints, baseline is defined as the last non-missing measurement prior to the first dose of double-blind study medication in 603B.
- For integrated endpoints by weeks from first exposure to bexagliflozin, baseline is defined as the last non-missing measurement prior to the first exposure of bexagliflozin. Considering the 4 sequences in Table 2, baseline for Seq 3 or 4 is the

last non-missing measurement prior to first dose of bexagliflozin in 603A. Baseline for Seq 1 or 2 is defined as the last non-missing measurement prior to the first dose of bexagliflozin in 603B run-in period. This applies to all integrated efficacy endpoints or the safety summaries by weeks of bexagliflozin treatment.

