### 9.2 Determination of Sample Size

The primary endpoint of study 603A is the change from baseline (Day 1) to week 12 in the 24-hour average SBP of the bexagliflozin group compared to the placebo group using a superiority testing at an overall two-sided 0.05 level of significance.

The primary endpoint of study 603B is the change from week 12 (cumulative week 24) to week 24 (cumulative week 36) in the 24-hour average SBP in the bexagliflozin group compared to the placebo group using a superiority testing at an overall two-sided 0.05 level of significance.

The assumptions to estimate the sample size for the primary endpoint of study 603A are:

1. The magnitude of the decrease from baseline (Day 1) to week 12 of the 24 h mean SBP in the bexagliflozin treatment arm will exceed that found in the placebo arm by 5 mm Hg;
2. The standard deviation of the change from baseline to week 12 will be 15 mm Hg for both the active and placebo groups;
3. The two-sided significance level is 0.05.

The assumptions to estimate the sample size required for the primary endpoint of study 603B are:

1. Bexagliflozin will remain effective for at least 24 weeks. The 24-hour average ABPM SBP will not change between week 12 and week 24 (cumulative week 24 and week 36).
2. Subjects who are randomized to receive placebo will show an increase in the ABPM SBP of 4 mm Hg between week 12 and week 24 (cumulative week 24 and week 36).
3. The standard deviation of the change is 15 mm Hg for both the active and placebo groups.
4. The two-sided significance level is 0.05.

A sample size of 254 per arm is required for the measurement to have 85% power to attain significance for the second primary endpoint. It is estimated that 75% of subjects will have completed the 36 weeks of study treatment since the first randomization. Thus a total sample size of 680 subjects is planned for the first randomization. It is estimated that approximately 8% will drop out for the first 12 weeks. With a sample size of 626 subjects at the end of study 603A, it will provide >95% power for the first primary endpoint.

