3. STUDY OBJECTIVES

3.1. STUDY 603A

In study 603A, the effectiveness of bexagliflozin tablets, 20 mg, will be assessed in a study population randomized 1:1 to receive either active agent or placebo.

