3.7. DETERMINATION OF SAMPLE SIZE

The primary efficacy endpoint of study 603A is the change from baseline (Day 1) to week 12 in the 24-hour average SBP of the bexagliflozin group compared to the placebo group using superiority testing at an overall two-sided 0.05 level of significance.

The primary efficacy endpoint of study 603B is the change from week 12 to week 24 in the 24-hour average SBP in the bexagliflozin group compared to the placebo group using superiority testing at an overall two-sided 0.05 level of significance.

Although the patient population was anticipated to be nearly identical between the two studies, they were to be carried out as independent investigations with respect to their individual primary and secondary endpoints. The assumptions used to estimate the sample size for the primary endpoint of study 603A were:

1. The magnitude of the decrease from baseline (Day 1) to week 12 of the 24 h mean SBP in the bexagliflozin treatment arm will exceed that found in the placebo arm by 5 mm Hg;
2. The standard deviation of the change from baseline to week 12 will be 15 mm Hg for both the active and placebo groups;
3. The two-sided significance level is 0.05.

The assumptions to estimate the sample size required for the primary endpoint of study 603B were:

1. Bexagliflozin will remain effective for at least 24 weeks. The 24-hour average ABPM SBP will not change between Week 12 and Week 24.
2. Subjects who are randomized to receive placebo will show an increase in ABPM SBP of 4 mm Hg between Week 12 and Week 24.
3. The standard deviation of the change is 15 mm Hg for both the active and placebo groups.
4. The two-sided significance level is 0.05.

A sample size of 254 per arm is required for the measurement to have 85% power to attain significance for the second primary endpoint. It is estimated that 75% of subjects will have completed the 36 weeks of study treatment since the first randomization. Thus a total sample size of 680 subjects is planned for the first randomization. It is estimated that approximately 8% will drop out for the first 12 weeks. A sample size of 626 subjects at the end of the first 12 weeks will provide >95% power for the first primary endpoint.

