7.3. DEMOGRAPHIC AND OTHER BASELINE CHARACTERISTICS

Demographics and baseline characteristics will be descriptively summarized for all ITT analysis sets by treatment group for studies 603A, 603B, and integrated ITT analysis set. Key variables will include: age, gender, race, ethnicity, baseline vital signs (includes office pulse, SBP, DBP in sitting, supine, and standing positions, 24-hour mean ambulatory SBP and 24-hour mean ambulatory DBP), ECG measures (to include RR interval, PR interval, QRS duration, and QT interval), renal function (to include eGFR), body weight, BMI, initial randomization stratification factors (to include diabetic status [history of type 2 diabetes or not], baseline ABPM SBP [≥ 160 mm Hg or not], and renal function [eGFR ≥ 60 mL/min/1.73 m² or not]), and background antihypertensive medications (4 most common medication types determined by ATC class 4 and all other

antihypertensive medications). Separate demographic and baseline characteristics tables will be prepared for each study. Summary descriptive statistics by treatment will include counts and percentages for discrete variables and estimation of means, standard deviations, medians, inter-quartile range (Q1, Q3), minimum, and maximum for continuous variables. Subject age will be calculated in the clinical database as the age at date of informed consent in 603A. Summaries for integrated analyses will be presented by bexagliflozin 20 mg in 603A, placebo in 603A and entered 603B, and all subjects in integrated ITT analysis set. Subjects randomized to the placebo arm in 603A and did not enter 603B will also be summarized in a separate group.

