8.1.1.1. Primary Efficacy Analysis

Let $\mu_{\text{Bexagliflozin}, 12}$ and $\mu_{\text{PBO}, 12}$ represent the mean changes from baseline in 24-hour ambulatory SBP at Week 12 for bexagliflozin and placebo arm, respectively. The following hypotheses will be tested:

$$H_0: \mu_{\text{Bexagliflozin}, 12} = \mu_{\text{PBO}, 12} \text{ versus } H_1: \mu_{\text{Bexagliflozin}, 12} \neq \mu_{\text{PBO}, 12}$$

To test this hypothesis, an analysis of covariance (ANCOVA) will be applied to analyze the mean change in 24-hour average ABPM SBP. The ANCOVA model will include terms for diabetes status (history of type 2 diabetes mellitus [T2DM] or not), renal function (eGFR at screening as continuous variable), pre-treatment status (presently medicated for hypertension or not), randomized treatment, and the baseline 24-hour mean SBP as fixed effect covariates. Change from baseline will be the dependent variable. Analysis will be conducted on ITT analysis set. The last ABPM SBP post baseline will be used for the analysis.

Descriptive statistics (n, mean, Q1, median, Q3, SD, minimum, and maximum) will be reported by treatment group, along with the least squares means, differences between LS means, a 2-sided 95% confidence interval (CI) for each difference, p-value from the model effects.

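### The 603A primary ANCOVA could add pre-dose seated office SBP as a covariate: an optional, nearly free and probably small gain in precision, not an error

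*SAP*

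**What the plan says.** The ANCOVA in SAP 8.1.1.1 has terms for diabetes history, screening eGFR and medicated status, and ends with "randomized treatment, and the baseline 24-hour mean SBP as fixed effect covariates". No office pressure appears. The rule in SAP 6.2.1 is: "For study 603A endpoints, baseline is defined as the last non-missing measurement prior to the first dose of double-blind study medication in 603A". One ambulatory recording supplies that value, since a repeat replaces a failed attempt (SAP 3.10). The same recording decides entry at 135 mm Hg (Protocol 4.2).

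SAP Table 1 schedules vital signs at visits 1, 2 and 3, and SAP 9.5 places them before dosing. Protocol 6.7 averages two serial readings per visit. Seated SBP must meet the entry range at visits 1 and 2, so these data should be nearly complete.

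The SAP uses baseline office SBP descriptively (SAP 7.3: "baseline vital signs (includes office pulse, SBP, DBP in sitting, supine, and standing positions") and as the covariate in the office SBP models, where it replaces the ambulatory value (SAP 8.1.2.3 and 8.1.2.4). The exploratory heart rate, weight and HbA1c models (SAP 8.1.3.4 to 8.1.3.6) already carry a second baseline variable beside the endpoint's own.

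**The concern.** A single 24-hour recording measures a subject's usual pressure with error. Part of the predictable between-subject variation in week-12 ambulatory SBP therefore stays in the residual. Office readings taken before dosing carry further information about that usual pressure, and adjusting for a pre-randomization value does not bias the randomized comparison.

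What is at stake is precision only. The model is repeated in each subgroup level (SAP 8.1.1.3), in subjects on three or more antihypertensive types and in dippers and non-dippers (SAP 8.1.3.1 and 8.1.3.3), where numbers are smaller. The tipping-point imputation (SAP 8.1.1.2) also predicts missing week-12 values from the one recording.

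**Working it through.** **Inputs from the documents.** Test: "using a superiority testing at an overall two-sided 0.05 level of significance" (Protocol 9.2). Effect: the decrease "in the bexagliflozin treatment arm will exceed that found in the placebo arm by 5 mm Hg". Spread: "The standard deviation of the change from baseline to week 12 will be 15 mm Hg for both the active and placebo groups". Allocation: "randomized 1:1 to receive either active agent or placebo". Attrition: "It is estimated that approximately 8% will drop out for the first 12 weeks", so 680 × 0.92 = 625.6, or 626 (313 per arm).

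**The plan's own figure.** SE = 15 × √(2/313) = 1.199 mm Hg. Power = Φ(5/1.199 − 1.960) = Φ(2.210) = 98.6%, which agrees with the stated >95%. The 95% half-width is 1.960 × 1.199 = 2.35 mm Hg.

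**Effect of a cut q in residual variance.** Replace 15 by 15 × √(1 − q). This is conservative, because 15 is an unadjusted SD and the ANCOVA residual should be smaller. Equivalent N = 626/(1 − q).

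| q | SE | Half-width | Power at 5 mm Hg | Power at 4 mm Hg | Equivalent N |
|---|---|---|---|---|---|
| 0 | 1.199 | 2.350 | 98.6% | 91.6% | 626 |
| 1% | 1.193 | 2.338 | 98.7% | 91.8% | 632 |
| 4% | 1.175 | 2.303 | 98.9% | 92.6% | 652 |
| 9% | 1.144 | 2.242 | 99.2% | 93.8% | 688 |

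The 4 mm Hg column is illustrative. It is the class-wide systolic effect in the meta-analysis cited in Protocol section 1, where baseline SBP was around 130 mm Hg.

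**How large might q be?** The documents give no office-ambulatory correlation, no ABPM test-retest correlation and no ANCOVA residual SD, so everything below is assumed. Let ρ be the correlation of baseline with week-12 ABPM, and r the correlation of mean office SBP with ABPM at either time. Then

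q = [r(1 − ρ)]² / [(1 − r²)(1 − ρ²)].

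- ρ = 0.8, r = 0.3: 0.0036/0.3276 = 1.1%
- ρ = 0.6, r = 0.5: 0.04/0.48 = 8.3%
- ρ = 0.5, r = 0.6: 0.09/0.48 = 18.8%

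If office SBP correlates with week-12 ABPM only 0.8 times as strongly as with baseline ABPM, the numerator becomes [r(0.8 − ρ)]². This gives 0% at ρ = 0.8 and 0.0144/0.4096 = 3.5% at ρ = 0.6, r = 0.6.

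**With the entry cut-offs simulated** (office 140 to <180 mm Hg at visits 1 and 2, ABPM ≥135 mm Hg):

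- Correlation model, ρ 0.6 to 0.8, single-visit office correlation 0.3 to 0.5: 0.6% to 7.1%. At a single-visit correlation of 0.6: 5% to 16%. Adding ρ = 0.5 there gives 17% to 22%, but the three-visit mean then correlates about 0.7 with ABPM before selection, beyond the closed-form range.
- Error model (SD of usual 24-hour SBP 10 to 16, ABPM error 7 to 10.6, office-ambulatory gap 8 to 12, office error 8 mm Hg): 1.4% to 9.2% for the three-visit mean; 1.0% to 6.6% for visit 3 alone.
- Same type of model, with error shared between the baseline ABPM and the visit 2 and 3 readings: 1.3% to 7.3% if 30% of error variance is shared, 0.4% to 5.3% if 60%.

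The simulations compare against baseline ABPM alone. The increment over the full SAP model was not computed and may be smaller.

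**The case against.** The plan is sound as it stands. It adjusts for the endpoint's own baseline and represents every factor used to stratify the first randomization, in line with Protocol 9.5. Power exceeds 95%, and 603B, not 603A, sets enrolment: 254 per arm at 75% completion is 508/0.75, about 678, against 680 planned. The equivalent extra subjects therefore could not be saved in practice. All of this stands, and it is why the point is optional.

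A reader might treat the three office visits as independent further readings. The documents do not support that. Visits 2 and 3 are the start and end of the baseline ABPM, so day-level deviations may be shared. Visit 1 precedes the run-in and coincides with lifestyle counselling, and the values at visits 1 and 2 are restricted by the entry range.

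A blanket extension to every model that refers to 8.1.1.1 would also be wrong. In the office SBP model it would place two overlapping versions of baseline office SBP side by side, and for weight and HbA1c no gain has been shown.

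What survives is narrow: the information is already collected, its use carries essentially no cost, and the SAP itself uses a second baseline covariate in lesser analyses.

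**Conclusion.** The omission is real, and it lies in the model of SAP 8.1.1.1; the baseline definition in 6.2.1 is not at fault. Adding office SBP is an optional gain of uncertain, probably small, size: about 1% to 9% of residual variance in a middle range of assumed correlations, about 0% to 19% at the extremes, and possibly less after the other covariates and shared day-level error. At the planned effect, a cut of up to 9% is worth at most about 0.6 points of power. At 4 mm Hg, a 4% cut is worth about 1 point.

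A reader might infer that the primary analysis is biased, underpowered or known to lose a fixed share of its precision. None of these follows: the comparison is valid without the term, the stated power reproduces, and no document figure fixes the loss.

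**What to change.** In SAP 8.1.1.1, add mean seated office SBP over visits 1 to 3 (each visit being the average of its two serial readings) as a continuous covariate alongside baseline 24-hour mean SBP. Add it also to the imputation model in 8.1.1.2 and to the 603A ambulatory SBP analyses that reuse the primary model: the subgroups in 8.1.1.3, three or more antihypertensives in 8.1.3.1, and dippers and non-dippers in 8.1.3.3. Do not add it to the office blood pressure, weight or HbA1c models. Keep 6.2.1 for change scores.

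The change departs from the covariates named in Protocol 9.5, so record it in SAP section 12. Because SAP 3.8.2 and section 10 report the interim analysis as already done, blinded staff should make the change before final unblinding. The cost is a short SAP amendment and one model degree of freedom, with no new data.

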6.2.2. First Dose Date

In general, the first dose date for 603A will be the date that the first dose of study drug is administered after the first randomization. The first dose date for 603B will be the date that the first dose of study drug is administered after the second randomization. The first dose date for integrated analysis will be the date that the first dose of bexagliflozin is administered.

6.2.3. Last Dose Date

The date of the last dose will be recorded in CRF at Day -1, cumulative weeks 12, 24, and 36. The last dose date for 603A will be the date recorded at week 12 and 603B will be the one recorded at 603B week 24. The date of the last dose in integrated analyses will be the latest last dose dates for any bexagliflozin kit dispensed.

6.2.4. Study Day

Study Day is the number of days starting from the first administration of double-blind study drug in each study, which is counted as Study Day 1. If the assessment date is after the date of the first double-blind medication, the study day is calculated as date of assessment - date of the first dose administration + 1. If the assessment date is prior to the date of the first double-blind medication, the study day is calculated as date of assessment - date of the first dose administration.

6.2.5. Duration

Duration of treatment for each period will be determined as Duration = date of the last dose in the specific period minus date of the first dose date in the specific period plus 1.

6.2.6. The 24-hr Mean ABPM

The 24-hour mean ABPM is computed following the steps below:

- The mean for each clock hour on each day are computed as the average of all readings within the hour on that day, e.g. Day 1 hour 9 is the average of all values on Day 1 09:00 - 09:59. The measures on different days from same clock hour are considered as separate values.
- The 24-hour mean will be computed as the average all available hourly mean.

6.3. MISSING DATA

The handling of missing or incomplete data is described for each endpoint and data type (as needed) in Section 7 to 9.

6.4. ANALYSIS VISIT WINDOWS

No analysis visit windows will be used. For by visit safety analysis, the early termination (ET) visit will be included in the derivation of the end of the study visit. For efficacy analysis, unscheduled or ET visit will be used if the scheduled visit is missing, described in Section 8. Nominal visits will be used for scheduled visit. In case if there are multiple assessments for a visit, the later one will be used.

6.5. POOLING OF CENTERS

Analysis will not be pooled by center.

6.6. TERMINOLOGY USED IN SAP

In general, terms below will be used:

- “Weeks” refer to study week, unless cumulative week is specified;
- Analysis for 603B refers to after randomization in 603B. The bexagliflozin dosing period before randomization is referred to as the “603B run-in period”.

7. DEMOGRAPHIC, OTHER BASELINE CHARACTERISTICS AND MEDICATION

7.1. SUBJECT DISPOSITION AND WITHDRAWALS

Subject disposition data will be presented in list form. Separate disposition tables will present the number and percentage of subjects who complete each of the salient study milestones. The disposition table for study 603A will be presented by treatment in 603A and overall. Those milestones will be: signing of the informed consent, screen pass prior to 603A run-in, screen pass after 603A run-in, randomization to 603A, completion of 603A, entered into 603B run-in. Table for 603B will be presented first by treatment sequence, then by treatment in 603B, and lastly, overall. Milestones will be: completion of the 603B run-in, randomization to 603B, and completion of 603B. In addition, the number and percentage of subjects who require rescue medication will be listed for each overall treatment period, either 603A (Period 1), 603B run-in (Period 2), or 603B (Period 3).

The reasons for early withdrawal will be summarized.

Assignment to the analysis sets (safety, ITT) at study 603A, study 603B will be summarized.

7.2. SUBJECT ELIGIBILITY AND PROTOCOL DEVIATIONS

All subjects, including screen failure subjects before and after run-in, who do not meet the Inclusion/exclusion criteria, will be listed. A table will display the number of subjects who fail at screening or 603A run-in (non-randomized subjects) with a summary of the reasons for screen fail prior to randomization.

The number and percent of subjects who had any major deviation will be tabulated along with disposition tables for the ITT Analysis Set.

7.3. DEMOGRAPHIC AND OTHER BASELINE CHARACTERISTICS

Demographics and baseline characteristics will be descriptively summarized for all ITT analysis sets by treatment group for studies 603A, 603B, and integrated ITT analysis set. Key variables will include: age, gender, race, ethnicity, baseline vital signs (includes office pulse, SBP, DBP in sitting, supine, and standing positions, 24-hour mean ambulatory SBP and 24-hour mean ambulatory DBP), ECG measures (to include RR interval, PR interval, QRS duration, and QT interval), renal function (to include eGFR), body weight, BMI, initial randomization stratification factors (to include diabetic status [history of type 2 diabetes or not], baseline ABPM SBP [≥ 160 mm Hg or not], and renal function [eGFR ≥ 60 mL/min/1.73 m² or not]), and background antihypertensive medications (4 most common medication types determined by ATC class 4 and all other

antihypertensive medications). Separate demographic and baseline characteristics tables will be prepared for each study. Summary descriptive statistics by treatment will include counts and percentages for discrete variables and estimation of means, standard deviations, medians, inter-quartile range (Q1, Q3), minimum, and maximum for continuous variables. Subject age will be calculated in the clinical database as the age at date of informed consent in 603A. Summaries for integrated analyses will be presented by bexagliflozin 20 mg in 603A, placebo in 603A and entered 603B, and all subjects in integrated ITT analysis set. Subjects randomized to the placebo arm in 603A and did not enter 603B will also be summarized in a separate group.

7.4. MEDICAL HISTORY

Significant medical, allergies, intolerance, and surgical history, including dates of diagnoses and procedures and whether the condition is ongoing, if applicable, will be collected. Each condition will be recorded as a verbatim term, date of onset, date resolved, and a checkbox that indicates ongoing conditions. Significant surgical and medical history will be coded using the Medical Dictionary for Regulatory Activities (MedDRA) version 19.0 or above.

Medical and surgical history will be summarized for the safety analysis set by system organ class (SOC), and MedDRA preferred term (PT) for each study. Subject data will be listed. Medical history for 603B will be summarized by treatment received during withdrawal period.

Subject diabetic, renal, and cardiovascular disease histories will be summarized for all categorical variables by frequency and percentage for both studies in the safety analysis set. Cardiovascular disease histories for 603B will be summarized by treatment received during the withdrawal period, then further split by treatment sequence. Diabetic and renal disease histories for 603B will be summarized by treatment received during 603 withdrawal period.

7.5. MEDICATION

All medication will be coded using the World Health Organization Drug Dictionary (WHO-DD) version March 2016 or above. Preferred drug name, Anatomical/ Therapeutic/ Chemical (ATC) class will be reported for inclusion in the database.

Medication summaries based on ATC level 2, and the preferred drug names will be produced for the safety analysis set. The summaries will present for each study, by the frequency and percentage of subjects who used any medication in an ATC class, or any medication based on a single preferred drug name. Subjects will be counted only once for each medication class and each preferred drug name.

